9.6.3 Demographic and Baseline Characteristics

The comparability of the vaccination groups for each relevant demographic and baseline characteristic will be assessed by the use of summary tables. No statistical hypothesis tests will be performed on these characteristics. The number and percentage of participants screened and randomized and the primary reasons for screening failure and discontinuation will be displayed. Demographic variables (eg, age, race, and gender), baseline characteristics, and prior and concomitant vaccinations and therapies will be summarized by vaccination group either by descriptive statistics or categorical tables.

9.7 Interim Analyses

A periodic review of safety and tolerability data across the V114 Phase 3 adult program will be conducted by an independent, unblinded, external DMC. A description of the structure and function of the DMC, along with the timing and content of the safety review, will be outlined in the DMC charter. Information regarding the composition of the DMC is provided in Appendix 1. There are no plans to conduct an interim analysis of unblinded immunogenicity data in this study. However, unblinded immunogenicity data will be made available to the DMC upon request to enable a benefit-risk assessment.

The DMC will serve as the primary reviewer of the results of the ongoing safety reviews and will make recommendations for discontinuation of the study or protocol modifications to an executive committee of the Sponsor (see Appendix 1 for details on the Committees Structure for this study). If the DMC recommends modifications to the design of the protocol or discontinuation of the study, this Executive Oversight Committee (EOC) of the Sponsor (and potentially other limited Sponsor personnel) may be unblinded to results at the intervention level to act on these recommendations. The extent to which individuals are unblinded with respect to ongoing safety reviews will be documented by the external unblinded statistician. Additional logistical details will be provided in the DMC Charter.

Study enrollment is likely to be ongoing at the time of external DMC review. Blinding to intervention assignment will be maintained at all investigational sites. Participant-level unblinding will be restricted to an external unblinded statistician performing ongoing safety reviews. Intervention-level ongoing safety reviews will be provided by the external unblinded statistician to the DMC. Prior to final study unblinding, the external unblinded statistician will not be involved in any discussions regarding modifications to the protocol, statistical methods, identification of protocol deviations, or data validation efforts after the safety reviews.

9.8 Multiplicity

The study will have met its primary immunogenicity objectives if noninferiority is demonstrated with respect to the OPA GMTs for the 13 shared serotypes and superiority is demonstrated with respect to both OPA GMTs and the proportions of participants with ≥ 4 -fold rises in OPA responses for the 2 unique serotypes. All hypotheses will be tested individually for each serotype at a 1-sided 0.025 alpha-level. This approach controls the 1-sided type-I error rate at 0.025, and no multiplicity adjustment will be required.

No multiplicity adjustments will be made for the safety comparisons.

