Multiplicity	
The study will be considered to have met its primary immunogenicity objectives if noninferiority is demonstrated with respect to OPA GMTs for the 13 shared serotypes and superiority is demonstrated with respect to both OPA GMTs and the proportions of participants with ≥ 4-fold rises in OPA responses for the 2 unique serotypes. Since comparisons are made individually for each of the 15 serotypes, this approach controls the 1-sided type-I error rate at 0.025, and no multiplicity adjustment is required.
 
No multiplicity adjustments will be made for the safety comparisons.

Sample Size and Power	This study will randomize approximately 600 participants into the V114 group and 600 participants into the Prevnar 13™ group. The overall power for all the primary hypotheses is >90% at an overall 1-sided 2.5% alpha-level.
------------------------------	--

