The second primary objective (proportions of participants with a ≥ 4 -fold rise from prevaccination to 30 days postvaccination for OPA responses for participants administered V114 versus participants administered Prevnar 13TM) will be assessed via the following superiority hypotheses for the 2 serotypes that are unique to V114:

$$\begin{aligned} H_0: p_1 - p_2 &\leq 0.1 \text{ versus} \\ H_1: p_1 - p_2 &> 0.1 \end{aligned}$$

where p_1 is the proportion of participants with a ≥ 4 -fold rise for the V114 group and p_2 is the proportion for the Prevnar 13TM group. A difference of 0.1 corresponds to the V114 group having a 10% higher proportion of participants with a ≥ 4 -fold rise in OPA responses from prevaccination to 30 days postvaccination than the Prevnar 13TM group. Rejecting the null hypotheses (H_0) at the 1-sided $\alpha=0.025$ level corresponds to the lower bound of the 2-sided 95% CI on the difference (V114 - Prevnar 13TM) being >0.1 and would lead to the conclusion that the proportion of participants with a ≥ 4 -fold rise in OPA responses in the V114 group for the unique serotype is superior to that in the Prevnar 13TM group.

To address the second primary immunogenicity objective, the serotype-specific proportion of participants with a ≥ 4 -fold rise will be compared between vaccination groups. Comparisons will be made through the estimation of the difference in the serotype-specific proportion of participants with a ≥ 4 -fold rise for each of the 2 unique serotypes in V114. Estimation of the proportion difference and 95% CI and the hypothesis test (ie, 1-sided p-value) will be conducted using the stratified M&N method (1985), an unconditional, asymptotic method [Miettinen, O. and Nurminen, M. 1985].

Secondary Endpoints/Hypotheses (H4)

The first secondary objective (to compare the serotype 3 OPA GMTs at 30 days postvaccination with V114 versus Prevnar 13TM) will be assessed via the following superiority hypotheses:

$$\begin{aligned} H_0: \text{GMT}_1 / \text{GMT}_2 &\leq 1.2 \text{ versus} \\ H_1: \text{GMT}_1 / \text{GMT}_2 &> 1.2 \end{aligned}$$

where GMT_1 is the serotype 3 OPA GMT for the V114 group and GMT_2 is the serotype 3 OPA GMT for the Prevnar 13TM group. A ratio of 1.2 corresponds to the V114 group having an OPA GMT that is 1.2-fold higher than the OPA GMT in the Prevnar 13TM group.

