Rejecting the null hypotheses (H_0) at the 1-sided $\alpha=0.025$ level corresponds to the lower bound of the 2-sided 95% CI on the GMT ratio ($V114/ \text{Prevnar } 13^{\text{TM}}$) being >1.2 and would lead to the conclusion that the serotype 3 OPA GMT in the V114 group is superior to the serotype 3 OPA GMT in the Prevnar 13TM group.

To address the first secondary immunogenicity objective, a cLDA method similar as the one used for the first primary immunogenicity objective (H1 and H2) will be used.

Secondary Endpoints/Hypotheses (H5)

The second secondary objective (proportion of participants with a ≥ 4 -fold rise from prevaccination to 30 days postvaccination for OPA responses for participants administered V114 versus participants administered Prevnar 13TM) will be assessed via the following superiority hypotheses for serotype 3:

$$H_0: p_1 - p_2 \leq 0 \text{ versus}$$

$$H_1: p_1 - p_2 > 0$$

where p_1 is the proportion of participants with a ≥ 4 -fold rise for the V114 group and p_2 is the proportion for the Prevnar 13TM group. A difference of 0 corresponds to no difference in the proportions of participants with a ≥ 4 -fold rise of OPA responses from prevaccination to 30 days postvaccination between V114 and Prevnar 13TM. Rejecting the null hypotheses (H_0) at the 1-sided $\alpha=0.025$ level corresponds to the lower bound of the 2-sided 95% CI on the difference ($V114 - \text{Prevnar } 13^{\text{TM}}$) being >0 and would lead to the conclusion that the proportion of participants with a ≥ 4 -fold rise in serotype 3 OPA responses in the V114 group is superior to that in the Prevnar 13TM group.

To address the second secondary immunogenicity objective, the stratified M&N method used for the second primary immunogenicity objective (H3) will be used.

Other Secondary Endpoints

A similar statistical model as used for the first primary objective will be used to address the secondary objective that evaluates the serotype-specific IgG GMCs at 30 days postvaccination with V114 compared with Prevnar 13TM.

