Descriptive statistics with point estimates and within-group 95% CIs will be provided for all other immunogenicity endpoints. For the continuous endpoints, the point estimates will be calculated by exponentiating the estimates of the mean of the natural log values and the within-group CIs will be derived by exponentiating the bounds of the CIs of the mean of the natural log values based on the t-distribution. For the dichotomous endpoints, the within-group CIs will be calculated based on the exact method proposed by Clopper and Pearson [CLOPPER, C. J. and PEARSON, E. S. 1934].

Reverse Cumulative Distribution Curves for both OPA titers and IgG concentrations at 30 days postvaccination with V114 will be graphically displayed by serotype.

A detailed analysis strategy for immunogenicity endpoints is listed in **Table 4**.

Table 4 Analysis Strategy for Immunogenicity Variables

Endpoint/Variable (Description, Time Point)	Primary vs. Supportive Approach [†]	Statistical Method [‡]	Analysis Population	Missing Data Approach
Primary Endpoint				
OPA GMTs at Day 30	P	cLDA [§] (estimate, 95% CI, p-value)	PP	Model-based
	S		FAS	
Proportions of participants with a ≥ 4 -fold rise from prevaccination to 30 days postvaccination for OPA responses for the 2 unique serotypes in V114	P	Stratified M&N (estimate, 95% CI, p-value)	PP	Missing data will not be imputed
	S		FAS	
Secondary Endpoint				
OPA GMTs at Day 30 for serotype 3	P	cLDA [§] (estimate, 95% CI, p-value)	PP	Model-based
Proportions of participants with a ≥ 4 -fold rise from prevaccination to 30 days postvaccination for serotype 3 OPA responses	P	Stratified M&N (estimate, 95% CI, p-value)	PP	Missing data will not be imputed
IgG GMCs at Day 30	P	cLDA [§] (estimate, 95% CI)	PP	Model-based
GMFRs and proportions of participants with a ≥ 4 -fold rise from baseline to 30 days postvaccination for both OPA and IgG responses	P	Descriptive Statistics (estimate, 95% CI)	PP	Missing data will not be imputed

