9.9 Sample Size and Power Calculations

9.9.1 Sample Size and Power for Immunogenicity Analyses

This study will randomize approximately 600 participants into the V114 group and 600 participants into the Prevnar 13™ group and has >90% power for demonstrating noninferiority to Prevnar 13™ for the 13 shared serotypes and superiority for the 2 unique serotypes for V114 at an overall 1-sided 2.5% alpha-level. Sample size is also driven by country-specific requirements (see Appendix 10.7 for details).

The sample size and power calculations are based on the following assumptions:

- 90% evaluability rate (approximately 540 evaluable participants per treatment group).
- The underlying serotype-specific OPA GMT ratios (V114/Prevnar 13™) for the 15 pneumococcal serotypes are the same as that observed in V114-006, which range from 0.78 to 1.86 across the shared serotypes and >6.0 for the V114 unique serotypes.
- The underlying differences (V114 - Prevnar 13™) between proportions of participants with a ≥ 4 -fold rise from prevaccination (Day 1) to 30 days postvaccination (Day 30) for OPA responses are the same as that observed in V114-006 for the V114 unique serotypes, which are >0.1.
- The variabilities for OPA titers in both the V114 group and Prevnar 13™ group are the same as those observed in V114-006. That is, the standard deviations of the natural log titers for the 15 pneumococcal serotypes range from 1.33 to 2.24 for V114 and range from 1.37 to 2.25 for Prevnar 13™.
- The statistical criteria for noninferiority and superiority require the lower bound of the 2-sided 95% CI of the OPA GMT ratio (V114/ Prevnar 13™) to be greater than 0.50 and 2.0, respectively.
- The statistical criterion for superiority requires the lower bound of the 2-sided 95% CI of the difference (V114 - Prevnar 13™) in the proportion of participants with a ≥ 4 -fold rise in OPA response to be greater than 0.1 for the serotypes unique to V114.

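### Sections 9.8 and 9.1 do not limit the 0.025 error statement to the primary decision, and the serotype 3 superiority tests (H4, H5) have no precondition, order or alpha split

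*Combined protocol and SAP*

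**What the plan says.** Section 9.8 sets one success rule, for the primary immunogenicity objectives. Noninferiority on OPA GMT is needed for all 13 shared serotypes, and superiority on both GMT and 4-fold rise for both unique serotypes. It then states: "All hypotheses will be tested individually for each serotype at a 1-sided 0.025 alpha-level. This approach controls the 1-sided type-I error rate at 0.025". The Multiplicity row of Section 9.1 repeats the rule and gives a reason: "Since comparisons are made individually for each of the 15 serotypes, this approach controls the 1-sided type-I error rate at 0.025".

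Two power statements mention an overall level. Section 9.1 has "The overall power for all the primary hypotheses is >90% at an overall 1-sided 2.5% alpha-level". Section 9.9.1 speaks of noninferiority for the shared serotypes and "superiority for the 2 unique serotypes for V114 at an overall 1-sided 2.5% alpha-level".

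H4 and H5 are numbered secondary hypotheses for serotype 3. Section 9.6.1 gives each its own null (GMT ratio at most 1.2; difference in proportions at most 0) and its own rejection rule at one-sided 0.025. For H4, rejection "would lead to the conclusion that the serotype 3 OPA GMT in the V114 group is superior". For H5, the conclusion is that the proportion with a 4-fold "rise in serotype 3 OPA responses in the V114 group is superior to that" in the comparator group. Table 4 asks for a p-value in the row "OPA GMTs at Day 30 for serotype 3" and in the serotype 3 fold-rise row, but only an estimate and interval for the IgG GMCs.

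Section 9.6.1 numbers these objectives, as in "The first secondary objective (to compare the serotype 3 OPA GMTs at 30 days postvaccination". The ordinals are labels, and no section presents them as a testing order. No section makes H4 or H5 depend on the primary decision or divides alpha between them.

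**The concern.** Testing each serotype individually at 0.025 fixes the error of each test. It does not fix the error of a set of claims. What protects the primary decision is that all its tests must pass, and Section 9.1 does not give that as the reason.

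H4 and H5 lie outside that rule. As written, a superiority conclusion over the licensed comparator for serotype 3 could be drawn after the primary decision has failed, or drawn from whichever of the two tests passes. Because Section 9.8 refers to all hypotheses, and serotype 3 is one of the 15 serotypes named in Section 9.1, a reader could take such a conclusion as covered by the stated 0.025 control. It is not.

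**Working it through.** **Inputs from the documents.** One-sided alpha 0.025 per test (9.8); all-must-pass primary rule (9.8); margins 1.2 for H4 and 0 for H5 (9.6.1); 540 evaluable per arm and SDs of natural log titer from 1.33 to 2.25 across both groups (9.9.1); primary power above 90% (9.1). **Assumed:** correlations between test statistics, which the documents do not give, so a range is shown.

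**1. The plan's own figure.** The primary decision has 13 + 2 + 2 = 17 component tests. If at least one null is true, the decision can be met only if that test falsely rejects. The worst case has one component at its margin and the other 16 certain to pass: 1 − Φ(1.960) = 0.025. The stated figure is reproduced for this decision.

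**2. Primary decision plus one serotype 3 test.** One primary null is at its margin with every other primary test passing, and one serotype 3 null is at its margin. The chance of at least one false claim is 1 − P(both statistics below 1.960), bivariate normal:

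| Correlation | At least one false claim |
|---|---|
| 0 | 1 − 0.975² = 0.0494 |
| 0.3 | 0.0476 |
| 0.5 | 0.0454 |
| 0.7 | 0.0417 |
| 0.8 | 0.0390 |

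**3. All three at their margins.** With both serotype 3 nulls at their margins as well, independence gives 1 − 0.975³ = 0.0731, and the bound is 3 × 0.025 = 0.075.

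**4. Can both serotype 3 nulls be at their margins?** Not if the V114 titer distribution is the comparator's shifted on the log scale.

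- At a true ratio of 1.2 the response proportion is higher with V114, so the H5 null is false.
- At a true ratio of 1.0 the H5 null is at its margin and H4 is well inside its null. P(H4 passes) = Φ(−ln 1.2 / SE − 1.960), with SE = SD × √(2/540). At SD 1.33, SE = 0.0809 and the probability is about 0.00001. At SD 2.25, SE = 0.1369 and it is about 0.0005. This uses a plain two-sample standard error.
- The pair's error at ratio 1.0 is therefore at most about 0.025 + 0.0005 = 0.0255. Simulations with assumed response rates and correlations gave 0.0226 to 0.0242.

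If the two distributions differ in spread, both nulls can sit at their margins. Simulations of that case, with an assumed comparator SD of 1.3 and an assumed 5-fold or 8-fold mean rise, gave about 0.040 for the pair.

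**5. With a precondition.** If H4 and H5 may be claimed only after the primary decision is met, any claim while a primary null is true needs a false primary pass, so the error is at most 0.025. If the primary is truly met, a valid method for the pair holds it at 0.025.

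**6. Power cost.**

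- Precondition: P(H passes and primary passes) ≥ P(H passes) − P(primary fails). The last term is below 0.10 by Section 9.1.
- Split of 0.0125 each: the largest loss is the maximum over δ of Φ(δ − 1.960) − Φ(δ − 2.241). It falls at δ = 2.10, where power is 0.556 against 0.444, a loss of 11.2 points.
- Both together: at most 10 + 11.2, about 21 points.

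**The case against.** The natural reading of Section 9.8 is that it concerns the primary objectives only. The paragraph opens with their success rule, and the 15 serotypes in Section 9.1 are the 13 shared plus the 2 unique serotypes of that same rule. The power statements in 9.1 and 9.9.1 tie the overall 2.5% to the primary tests. The plan nowhere expressly claims study-wide control, and control across secondary hypotheses is partly a matter of choice. This stands as far as intent goes. A reader might infer that the plan expressly claims control for H4 and H5, and the documents do not support that. But the primary-only reading does not settle the matter. On that reading, H4 and H5 still end in superiority conclusions with no error control beyond each single test, and nothing calls them nominal.

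The plan also has a partial safeguard. H4 and the serotype 3 part of H1 use the same GMT ratio interval (Table 4 gives both the same model). A lower bound above 1.2 is also above 0.5, so H4 cannot pass if serotype 3 fails noninferiority. It can still pass when another of the 17 tests fails.

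Finally, the 4.9% case is extreme. Under the planning assumptions in 9.9.1 (shared ratios 0.78 to 1.86 against 0.5; unique above 6.0 against 2.0) no GMT primary null is true. This also stands, and the figures are worst cases.

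**Conclusion.** The point holds. The 0.025 statement is correct for the Section 3 primary decision, but it is not worded as limited to that decision, and 9.1 gives the wrong reason for it. H4 and H5 can each yield a formal superiority conclusion that the all-must-pass rule does not cover.

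The worst-case joint error is 4.9% for the primary decision plus one serotype 3 test, if independent, and less with positive correlation. It reaches 7.3% (bound 7.5%) only if both serotype 3 nulls are at their margins too, which a pure shift excludes. Under a pure shift the H4/H5 pair alone stays near 2.5%.

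Two stronger readings are not supported. A reader might infer that the primary conclusion has inflated error; it does not. A reader might also infer that only the Section 3 decision holds 0.025. In fact each of H4 and H5 holds it singly, and so does the separate H1 to H3 decision for participants 65 and older in Appendix 7 when taken by itself, by the same all-must-pass argument.

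This should be fixed, but it does not touch the primary conclusion, the sample size or any estimate.

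**What to change.** Amend Sections 9.8 and 9.1 before unblinding; the opening of Section 9 already requires an amendment for changes to methods tied to hypotheses. Suggested content:

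- The requirement that all tests pass controls the one-sided type I error of the Section 3 primary immunogenicity decision (H1 to H3, all participants) at 0.025. This replaces individual comparison as the stated reason.
- H4 and H5 are tested for a confirmatory claim only if that decision is met, by one prespecified method, for example a fixed sequence in a stated order at one-sided 0.025, or Holm. Otherwise their results are nominal.
- If the sponsor does not want the precondition, keep the limited 0.025 sentence and label H4 and H5 nominal.

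The choice of method is the sponsor's. The precondition removes the 4.9% case, and the method for the pair covers departures from a pure shift.

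Cost: no more participants and no effect on the primary. The precondition costs H4 or H5 less than 10 points of power if the stated primary power is right. A 0.0125 split costs at most 11.2 points, Holm no more than that, and precondition plus split at most about 21. In a fixed sequence the leading hypothesis pays only for the precondition, while the other is also lost whenever the leading one fails. The nominal label costs no power but gives up a confirmatory serotype 3 claim.

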9.9 Sample Size and Power Calculations

9.9.1 Sample Size and Power for Immunogenicity Analyses

This study will randomize approximately 600 participants into the V114 group and 600 participants into the Prevnar 13™ group and has >90% power for demonstrating noninferiority to Prevnar 13™ for the 13 shared serotypes and superiority for the 2 unique serotypes for V114 at an overall 1-sided 2.5% alpha-level. Sample size is also driven by country-specific requirements (see Appendix 10.7 for details).

The sample size and power calculations are based on the following assumptions:

- 90% evaluability rate (approximately 540 evaluable participants per treatment group).
- The underlying serotype-specific OPA GMT ratios (V114/Prevnar 13™) for the 15 pneumococcal serotypes are the same as that observed in V114-006, which range from 0.78 to 1.86 across the shared serotypes and >6.0 for the V114 unique serotypes.
- The underlying differences (V114 - Prevnar 13™) between proportions of participants with a ≥ 4 -fold rise from prevaccination (Day 1) to 30 days postvaccination (Day 30) for OPA responses are the same as that observed in V114-006 for the V114 unique serotypes, which are >0.1.
- The variabilities for OPA titers in both the V114 group and Prevnar 13™ group are the same as those observed in V114-006. That is, the standard deviations of the natural log titers for the 15 pneumococcal serotypes range from 1.33 to 2.24 for V114 and range from 1.37 to 2.25 for Prevnar 13™.
- The statistical criteria for noninferiority and superiority require the lower bound of the 2-sided 95% CI of the OPA GMT ratio (V114/ Prevnar 13™) to be greater than 0.50 and 2.0, respectively.
- The statistical criterion for superiority requires the lower bound of the 2-sided 95% CI of the difference (V114 - Prevnar 13™) in the proportion of participants with a ≥ 4 -fold rise in OPA response to be greater than 0.1 for the serotypes unique to V114.

